12.4.3 Handling of missing values/censoring/discontinuations

Missing data for primary and secondary endpoints will be addressed using multiple imputation.

As these endpoints are binary outcomes derived from underlying continuous variables, the imputations will be performed on those continuous variables, from which the imputed binary outcomes will then be constructed. Subjects who discontinue from study treatment early will be encouraged to stay in the study and are considered as retrieved dropout (RDO) subjects. The analysis will account for different post-randomization events for missing data handling as follows:

Permanent discontinuation of study treatment due to AE (Adverse Event), LoE (Lack of Efficacy): If retrieved dropout data are available, these will be used for analysis. If no data was retrieved after study treatment discontinuation, missing data will be multiply imputed based on placebo arm data ([Carpenter et al 2013](#)). More details on the imputation model will be specified in the Statistical Analysis Plan prior to unblinding.

Permanent discontinuation of study treatment due to other reasons than AE (Adverse Event), LoE (Lack of Efficacy): If efficacy data collected after study treatment discontinuation are available (retrieved dropout), then the retrieved drop-out data will be excluded and missing data after study treatment discontinuation will be multiply imputed using the MAR (missing at random) assumption. In case of a major health event (e.g. pandemic/epidemic), the number of missing measurements may increase and the potential to recover information for the main endpoints from intermediate measurements that have been dropped from the visit schedule may decrease. This may affect the power of tests and the precision of estimates for this study.

Furthermore, the Sponsor might consider additional analyses to assess any potential impact of a major health event on our study results. Detailed information, including missing data handling plan and additional analysis will be specified in the Statistical Analysis Plan.

12.4.4 Sensitivity and Supportive analyses

Sensitivity analyses

To further support the primary estimand, sensitivity analyses will be considered in the way of varying assumptions about the missing outcomes between treatment arms.

Another sensitivity analysis will be performed where the baseline is defined as weighted average of first screening visit (with weight 1/6) and the second screening visit (with weight 2/6) and the randomization visit (with weight 3/6). This weighted average is being used during the study to identify the need for rescue medication and it is also used at Week 52 to identify responders being randomized in the extension study.

Supportive analyses

A supplementary estimand, which is detailed in the Statistical Analysis Plan, and following analyses will also be done to support primary endpoints:

- The number and percentage of subjects will be presented for proportions of subjects who achieved at least 50%, 75% and 100% reductions in the AN count relative to Baseline (AN50, AN75, AN100).
- Summary statistics will be presented for absolute and percent change from Baseline in AN count.
- Summary statistics will be presented for absolute and percent change from Baseline in number of abscesses.
- Summary statistics will be presented for absolute and percent change from Baseline in number of inflammatory nodules.
- Summary statistics will be presented for absolute and percent change from Baseline in number of draining fistulas.

12.5 Analysis of secondary endpoints

12.5.1 Efficacy and/or Pharmacodynamic endpoint(s)

The secondary endpoints of this study are planned as follow:

- Percentage change from baseline in AN count at Week 16
- Flare over 16 weeks: Patients who experience at least one flare over 16 weeks. Flare is defined as an at least a 25% increase in AN counts with a minimum increase of 2 AN relative to baseline.
- Pain/NSR30 at Week 16: Patients achieving NRS30 at Week 16, among patients with baseline NRS \geq 3. NRS30 is defined as at least 30% reduction and at least 2 unit reduction from baseline in Patient's Global Assessment of Skin Pain. NRS from baseline to Week 16 is the weekly average score calculated based on the 7 available daily scores: Baseline (Week 0) will be average of NRS score from day -7 to day -1, week 1 will be average of

score from day 1 to day 7, week 2 will be average of score from day 8 to day 14 and so on. For any week with less than 4 diary entries within the week, the weekly average will be recorded as missing.

For the secondary endpoint of percentage change in AN count from baseline to Week 16, an analysis of covariance (ANCOVA) model will be fitted to estimate the treatment differences between the two secukinumab regimens and placebo with treatment group, baseline AN count, Hurley stage, use of antibiotic, geographical region and baseline body weight as covariates.

The analysis method for both flare up to Week 16 and Pain/NRS30 at Week 16 will be the logistic regression: with treatment group, Hurley stage, geographical region, use of antibiotic, baseline body weight and baseline AN counts as explanatory variables for flare endpoints; and with treatment group, Hurley stage, region, use of antibiotic, baseline body weight and baseline NRS as explanatory variables for pain endpoints. Odds ratios will be computed for comparisons of secukinumab dose regimens versus placebo utilizing the logistic regression model fitted. In case of response rates of 0% or of 100% in one of the treatment groups, Fisher's exact test will be applied. Risk difference and confidence intervals for risk difference will be provided.

Testing strategy

Two studies of identical design (CAIN457M2301 and CAIN457M2302) are planned, each with multiple endpoints. Primary endpoint, secondary endpoints percentage change from baseline in AN count at Week 16 and flare over 16 weeks will be tested in each of the two studies separately. Pain/NRS30 at Week 16 will be tested using the combined data from the two studies. In order to control for the type-I error rate ("false positive rate") at the level of the individual studies, and at the level of the combined dataset of both studies, the testing strategy illustrated in [Figure 12-1](#) below will be implemented.

The hypotheses included in the test procedure are listed below:

Primary endpoint (as described in [Section 12.4](#)):

H1(H'1): secukinumab 300 mg q2w s.c. is not different to placebo regimen with respect to HiSCR after 16 weeks of treatment.

H2(H'2): secukinumab 300 mg q4w s.c. is not different to placebo regimen with respect to HiSCR after 16 weeks of treatment.

Secondary endpoints:

H3(H'3): secukinumab 300 mg q2w s.c. is not different to placebo regimen with respect to percentage change from baseline in AN count at Week 16

H4(H'4): secukinumab 300 mg q4w s.c. is not different to placebo regimen with respect to percentage change from baseline in AN count at Week 16

H5(H'5): secukinumab 300 mg q2w s.c. is not different to placebo regimen with respect to flare over 16 weeks of treatment

[figure not shown]
H6(H'6): secukinumab 300 mg q4w s.c. is not different to placebo regimen with respect to flare over 16 weeks of treatment

H7: secukinumab 300 mg q2w s.c. is not different to placebo regimen with respect to NRS30 at Week 16

H8: secukinumab 300 mg q4w s.c. is not different to placebo regimen with respect to NRS30 at Week 16

Efficacy of two secukinumab regimens compared to placebo with respect to percentage change from baseline in AN count at Week 16 could be demonstrated if H3(H'3) and/or H4(H'4) is/are rejected and the treatment effect is in favor of Secukinumab. Efficacy of two secukinumab regimens compared to placebo with respect to flare over 16 weeks could be demonstrated if H5(H'5) and/or H6(H'6) is/are rejected and the treatment effect is in favor of secukinumab. Efficacy of two secukinumab regimens compared to placebo with respect to Pain/NSR30 at Week 16 could be demonstrated if H7 and/or H8 is/are rejected and the treatment effect is in favor of secukinumab.

Figure 12-1 Testing strategy

Testing procedure and type-I-error control in the planned submission includes studies CAIN457M2301 and CAIN457M2302 (both with identical design). Hypotheses can only be tested in the order as indicated by the arrows. The hypothesis H1 of the primary objective (HiSCR at Week 16) for the high dose secukinumab regimen (q2w) versus placebo will be tested at $4\alpha/5$ while the hypothesis H2 of the primary objective (HiSCR at Week 16) for the low dose secukinumab regimen (q4w) versus placebo will be tested at $\alpha/5$ simultaneously. If at least one of H1 and/or H2 are/is rejected then H3 and/or H4 (percentage change from baseline in AN count at Week 16), is tested. If at least one of H3 and/or H4 are/is rejected, then the corresponding alpha will be passed to H5 and/or H6 (flare over 16 weeks) respectively. Once HiSCR, percentage change in AN count and flare hypotheses for a secukinumab regimen are rejected, the respective $4\alpha/5$ for the high dose and $\alpha/5$ for the low dose can be passed on to the other regimen's hypotheses, if they are not already rejected at the initial significance level (i.e., $\alpha/5$ for the low dose and $4\alpha/5$ for the high dose). If both studies independently reject the primary null-hypothesis on the same secukinumab regimen (H1 and H'1, or H2 and H'2), then the corresponding secukinumab regimen's pain hypothesis (H7 or H8) can be tested. Additionally,

the significance level for the pain hypothesis can be passed from one dose regimen to the other dose regimen if one pain dose regimen is rejected and the primary null-hypothesis on the two secukinumab regimen are all rejected. The initial significance level for pain hypothesis (H7 and/or H8) is set to $\alpha-\alpha^2$. The subtraction of α^2 is to account for the maximum possible type I error to claim a success for HiSCR, percentage change in AN count and flare in both studies. Therefore, the type I error rate is controlled at level α for the submission on all hypothesis endpoints. The detailed information regarding the significance level of H7 and H8 can be found in [Section 16.3](#) (Appendix 3: Type I alpha for the pain hypothesis). Under the global null hypothesis (i.e. no difference between secukinumab and placebo), the testing procedure outlined above controls the type I error rate (one-sided) at the study-level to <0.025 , and at the submission level to $<0.000625(=0.025^2)$. Considering all possible configurations of true and false null hypotheses, the type I error control at the level of the submission is <0.000625 for the primary objectives, and <0.025 for all hypotheses ([Bretz et al 2019](#)).

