12.8 Sample size calculation

Sample size requirements for this study are primarily driven by HiSCR at Week 16 endpoints. A 5% two-sided type-I-error rate will be used to control for type I error. Two secukinumab doses will be tested versus placebo with respect to the primary endpoint (HiSCR at Week 16). The type-I-error will be split to 4% and 1% two-sided for secukinumab 300 mg q2w vs. placebo and secukinumab 300 mg q4w vs. placebo, respectively. Sample sizes will be based on this type-I-error assumption.

A total of 471 patients was originally planned to be randomized to study drug in a 1:1:0.5:0.5 ratio. A second study of identical design with the same sample size will be conducted in parallel. Both studies are independently powered to address the primary endpoint (HiSCR) and secondary endpoint on flare. The secondary endpoint on pain will be analyzed in the combined populations of both trials, provided the primary null-hypothesis can be rejected in both studies. All sample size calculations were done in nQuery Advisor 7.0.

As discussed in [Section 5](#), to account for the disruptive impact of the COVID-19 pandemic on the conduct of the study since the release of protocol amendment 01, the number of randomized patients was increased to approximately 541 (15% increase from the original population of 471 patients).

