12.8.2 Secondary endpoint(s)

The power mentioned for the Secondary endpoints is conditional on the successful rejection of the null hypothesis for the primary endpoint (HiSCR), and the testing procedures are defined in [Section 12.5.1](#).

Percentage change in AN count: based on adalimumab phase III placebo-controlled studies (PIONEER I and II, respectively ([Kimball et al 2016](#))), it is assumed that the difference between secukinumab and placebo is at least 18% in favor of secukinumab when considering the mean percentage change from baseline in AN count at Week 16. Although it is planned to use a repeated measures model for the analysis, an approximate sample size can be based on a simple t-test. The original sample size of 471 patients is sufficient to achieve 92% power in secukinumab 300 mg q2w vs. placebo and 81% power in secukinumab 300 mg q4w vs. placebo when assuming a standard deviation of 46%.

Flare: Based on adalimumab phase III placebo-controlled studies (PIONEER I and II, respectively, [Kimball et al 2016](#)), a placebo rate of 35% is assumed. The original sample size

of 471 patients is sufficient to achieve 98% power for the demonstration of 20% difference of secukinumab 300 mg q2w over placebo based on the second endpoint when assuming secukinumab 300 mg q2w rate to be 15%. Assuming the same rate for secukinumab 300 mg q4w, the sample size would be sufficient to achieve 92% power in a comparison of secukinumab 300 mg q4w vs. placebo.

Pain: Based on adalimumab phase III placebo-controlled studies (PIONEER I and II, respectively, [Kimball et al 2016](#)), a placebo rate of 23% is assumed. Assuming 80% patients are qualified to calculate Pain variable NRS30, the original total sample size of 942 patients across two studies is sufficient to achieve 85% power for the demonstration of 13% difference of secukinumab 300 mg q2w over placebo based on the second endpoint when assuming the rate to be 36%. The original sample size is also sufficient to achieve 70% power to demonstrate superiority of secukinumab 300 mg q4w over placebo based on the same assumptions in regards to the rates of secukinumab and placebo as above.

13 Ethical considerations and administrative procedures

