## Skin Pain/NRS30

The number and percentage of NRS30 responder subjects will be presented by visit up to Week 52 for each treatment group observed values will be presented.

Figures will be provided displaying estimates for responder rates by treatment groups including confidence intervals.

A similar MELRM analysis as described for HiSCR will be performed for this endpoint.

The endpoint is the achievement of NRS30 and all time points for time windows from Week 2 up to Week 52 are included on the left hand side of the model as dependent variables. The covariates included as fixed effects are: treatment group, visit, baseline NRS score and the interaction between visit and treatment group. An unstructured covariance structure will be applied. In case of non-convergence, alternative covariance structures will be considered. If

additional convergence issues are encountered, then modifications to the model will be considered.

Analyses will be performed at a study level and also pooling both studies.

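### The pooled NRS30 models (H7/H8 and the Week 52 MELRM) list no study term; adding one is a free, small gain in power, not the removal of a bias

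*Protocol*

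**What the plan says.** Protocol 12.5.1 (Testing strategy) states: "Pain/NRS30 at Week 16 will be tested using the combined data from the two studies". Appendix 3 (16.3) repeats that pain is analyzed on pooled data and gives the alpha for each scenario. The model in Protocol 12.5.1 is a logistic regression "with treatment group, Hurley stage, region, use of antibiotic, baseline body weight and baseline NRS as explanatory variables for pain endpoints". No study factor appears there or in the protocol summary.

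SAP 2.13 (Skin Pain/NRS30) fits a mixed effects logistic regression (MELRM) to NRS30 up to Week 52. Its fixed effects are treatment group, visit, baseline NRS and the visit-by-treatment interaction. It then says: "Analyses will be performed at a study level and also pooling both studies". SAP 5.4.2.2 gives the same list, again without study.

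SAP Section 1 leaves all analyses in the testing hierarchy to a separate Week 16 PEA SAP, which is not among the documents reviewed.

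**The concern.** Within each trial, randomization is stratified by region, antibiotic use and body weight (Protocol 6.3.2), and all three enter the Week 16 pain model. Once two separately randomized trials are pooled, study is a further randomization block, and it is the only design factor missing from the list. The list would be complete for a single-trial analysis, and pain is the only confirmatory endpoint that is pooled.

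H7 and H8 are alpha-controlled claims. If NRS30 rates differ between the trials, a logistic model without study estimates an odds ratio closer to 1 than the within-study value and gives up some power. H8 has least to spare, since Protocol 12.8.2 plans only 70% power for it.

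**Working it through.** **Inputs.** Protocol 12.8: "The type-I-error will be split to 4% and 1% two-sided for secukinumab 300 mg q2w vs. placebo", with 1% for q4w; allocation 1:1:0.5:0.5, hence 1:1:1 once the placebo arms are pooled; a second trial of the same design and size. Protocol 12.8.2: "a placebo rate of 23% is assumed"; "13% difference of secukinumab 300 mg q2w over placebo based on the second endpoint when assuming the rate to be 36" (percent); an evaluable share of 80% for NRS30; and, on size and power, "the original total sample size of 942 patients across two studies is sufficient to achieve 85% power".

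**Reproducing the plan's power.** Patients per arm: 942 × 0.80 / 3 = 251.2. With d = 0.13, the Fleiss continuity correction leaves n' = n − 2/d + 1/(d²n) = 251.2 − 15.38 + 0.24 = 236.05. Then z = [d√n' − z_α√(2p̄q̄)] / √(p0q0 + p1q1), where p̄ = 0.295.

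- q2w (4%): (1.9973 − 2.0537 × 0.6449) / 0.6384 = 1.054, so power is 85.4% (plan: 85%).
- q4w (1%): (1.9973 − 2.5758 × 0.6449) / 0.6384 = 0.526, so power is 70.1% (plan: 70%).

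Without continuity correction the figures are 87.6% and 73.4%. The plan's figures are reproduced.

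**With and without study.** Two equal trials, n = 125.6 per arm per study, a common within-study odds ratio of (0.36/0.64)/(0.23/0.77) = 1.883 (log 0.6329), and a mean placebo rate of 23%. The gap in placebo rate between the trials is an assumption, because neither document gives NRS30 rates by study. Large-sample Wald power, no other covariates:

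- With study: Φ(ln OR/SE_s − z_α), where SE_s = 1/√(I1 + I2) and I_k = 1/[1/(n·p0k·q0k) + 1/(n·p1k·q1k)].
- Without study: Φ((ln OR_m − z_α·SE_m)/SE_t). OR_m comes from the rates averaged over the trials, SE_m is the standard error that model reports, and SE_t is the true one, from the within-study variances.

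Worked case, 10-point gap. Placebo rates are 0.18 and 0.28; active rates are 0.2925 and 0.4227 (mean 0.3576). OR_m = (0.3576/0.6424)/(0.23/0.77) = 1.864, log 0.6226, a shrinkage of 1.6%.

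- Without study, SE_m = 0.1995 and SE_t = 0.1979. q2w: (0.6226 − 2.0537 × 0.1995)/0.1979 = 1.075, power 85.89%. q4w: (0.6226 − 2.5758 × 0.1995)/0.1979 = 0.549, power 70.85%.
- With study, I1 + I2 = 10.82 + 13.87 = 24.69 and SE_s = 0.2013. q2w: 0.6329/0.2013 − 2.0537 = 1.091, power 86.24%. q4w: 0.569, power 71.53%.

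| Placebo gap (points) | OR without study | q2w with / without | q4w with / without |
|---|---|---|---|
| 0 | 1.883 | 86.9% / 86.9% | 72.5% / 72.5% |
| 5 | 1.878 | 86.7% / 86.6% | 72.3% / 72.1% |
| 10 | 1.864 | 86.2% / 85.9% | 71.5% / 70.9% |
| 20 | 1.806 | 84.2% / 82.5% | 68.4% / 65.3% |
| 30 | 1.711 | 80.0% / 75.0% | 62.6% / 54.4% |

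From unrounded values the losses (q2w, q4w) are 0.35 and 0.7 points at a 10-point gap, 1.7 and 3.1 at 20, and 5.0 and 8.2 at 30.

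**Simulation** (10,000 trials per scenario, 126 per arm per study). At a 10-point gap the odds ratio is 1.873 without study against 1.895 with it; power is 87.0% v 87.4% (q2w) and 72.3% v 73.2% (q4w). At 20 points the odds ratio is 1.813 v 1.893, with power 83.6% v 85.3% and 66.0% v 69.4%. Direction and approximate size agree.

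**Type I error without study.** Under the null, the ratio of true to reported variance at a 10-point gap is [(0.18 × 0.82 + 0.28 × 0.72)/2]/(0.23 × 0.77) = 0.1746/0.1771 = 0.986. The actual size at nominal 0.04 is 2[1 − Φ(2.0537/√0.986)] = 0.0386. At 20 points the ratio is 0.1671/0.1771 = 0.944 and the size 0.0345. The simulated sizes are 0.0381 and 0.0335. The test is conservative, not liberal.

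**Sensitivity.** If both trials reach 541 patients (541 × 0.80 / 3 = 144.3 per arm per study), the 10-point gap gives 90.6% v 90.3% (q2w) and 78.7% v 78.1% (q4w).

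**The case against.** The strongest objection is that the document governing H7 and H8 has not been seen. The Week 16 PEA SAP may well include study, and the protocol list may be only a general description. This stands as a limit: the omission is shown only for the protocol and the Week 52 SAP. A study term in the PEA SAP would still leave the protocol's explicit list out of step with it. The imputation model is likewise deferred to a SAP, so no finding is made on it.

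The second objection is size. It also stands. At moderate gaps the loss is under one point, and region, Hurley stage, antibiotic use, weight and baseline NRS may absorb part of any difference between the trials.

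Four stronger readings are tempting, and the documents do not support them:

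- *That the omission biases the treatment effect or endangers the alpha control.* Both trials use the same allocation and size, so study is not associated with treatment by design. The model without study targets a marginal odds ratio, and its test remains valid.
- *That large between-trial gaps are to be expected.* Protocol 1.1 reports HiSCR rates of 41.8% and 58.9% on adalimumab in its two phase III trials, but the placebo rates were 26% and 27.6%, a gap of 1.6 points. With a 1.6-point placebo gap in the calculation above, power with and without study agrees to within 0.02 points. What differed there was the effect: the odds ratios are (0.418/0.582)/(0.26/0.74) = 2.0 and (0.589/0.411)/(0.276/0.724) = 3.8. A study main effect does not address that, and those rates are HiSCR, not NRS30.
- *That chance imbalance in study mix between arms matters materially.* It is possible in the subset with baseline NRS of at least 3 and diary data, but it has not been quantified.
- *That the Week 52 MELRM is attenuated in the same way.* The calculation is for a fixed-effects logistic model. If the MELRM has a subject random effect, much of a balanced study effect would go into that variance. It is also exploratory, and study-level results are reported alongside.

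**Conclusion.** The point holds as a minor one. The protocol's covariate list for the pooled H7/H8 regression and the pooled Week 52 NRS30 model both omit study, the randomization block that pooling creates. The consequence is some attenuation of the odds ratio, a slightly conservative test and a small power loss if NRS30 rates differ between trials. The range runs from nothing at equal rates to about 1.7 points (q2w) and 3.1 points (q4w) at a 20-point placebo gap, a gap for which the documents give no support. These figures assume equal trial sizes, a common within-study odds ratio of 1.883, the plan's 4% and 1% levels, and no help from other covariates, so they are nearer an upper range. Confidence is high about the text of the two documents and moderate about what will be done for H7/H8, because the PEA SAP was not available. For the Week 52 model the case is consistency only.

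**What to change.** In Protocol 12.5.1, state that the NRS30 logistic regression on the combined data (H7, H8) also contains study (CAIN457M2301 or CAIN457M2302) as a fixed factor. For consistency, add the same factor to the pooled NRS30 MELRM in SAP 2.13 and to the general model text in SAP 5.4.2.2 where data are pooled. The study-level models stay as they are. If the Week 16 PEA SAP already includes study, cite it and align the wording of the protocol and the Week 52 SAP.

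The cost is one model term, 1 degree of freedom among about 500 evaluable patients per comparison (2 × 251.2), and a few words of text. No new data are needed, and the alpha allocation does not change.
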